8.1 Definitions

An adverse event is an undesirable or unintentional event affecting the well-being of a subject that occurs during use of the study drug, whether or not considered related to the drug; this includes accidental injuries, reasons for any change in medication (drug and/or dose), and reasons for surgical procedures. It is to be noted that procedures are not adverse events. Abnormal laboratory values or clinically significant changes in laboratory values are not adverse events, but the underlying reasons are. Regardless of the severity or relationship to the investigational drug, all adverse events occurring during the study period must be recorded in the subject's eCRF.

An unexpected adverse event is one that has not been previously observed, or one that is of a specificity or severity not consistent with the current Investigator Brochure.

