3.4 Safety Parameters and Timing

Safety will be assessed during the study by collection of study events, review of concomitant treatments and laboratory data. Clinical adverse event reporting will be conducted at each visit.

All laboratory measurements will be performed by a central laboratory using appropriate and validated methods. Values will be reported to the Investigator and the Sponsor. Laboratory reference range values will be described in the laboratory manual. Investigators will assess all out of range values as being clinically significant or not.

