8 ADVERSE EVENT REPORTING

Adverse event reporting will be handled in accordance with the IRB requirements and the requirements of other regulatory authorities that may apply, e.g. the Food and Drug Administration.

Adverse Events reporting will be solicited by non-leading "How Do You Feel" questions. Subtle symptoms of local or systemic spread of toxin effect would be unlikely to be recognized by the subjects as related to treatment. Therefore, study participants will be asked if they experienced weakness, lethargy, or difficulty swallowing or breathing. In addition, information derived from change in concomitant medications, laboratory analyses, and clinical observations will be evaluated for possible indications for side effects. Adverse events resulting from concurrent illnesses or reactions to concurrent medications will also be recorded. The Investigator must monitor the condition of the subject throughout the study from the time of obtaining informed consent until the final study visit.

Any adverse event, including both observed and volunteered problems, complaints, and symptoms, will be recorded on the Adverse Event pages of the electronic Case Report Form. When an adverse event occurs, the following information and assessments should be recorded in the adverse event section of the eCRF:

- The signs, symptoms or diagnosis or the event,
- The date and time of onset of the event using the 24-hour clock where midnight is 00:00 and noon is 12:00. Onset is the date when the first sign or symptoms were first noted.
- Date of recovery/ resolution
- The adverse event severity/ intensity using the criteria outlined in Section 8.1.2
- The relationship of the event to the study drug as outlined in Section 8.1.1

- Any other actions required such as therapy, medication, treatment or diagnostic procedure
- Seriousness of the event using the criteria outlined in Section 8.1.3
- Outcome (recovered, recovered with sequelae, not yet recovered, death)

Follow-up of a subject should be conducted until resolution of the adverse event or until the medical condition is stable. The investigator is responsible for the appropriate medical management of all adverse events.

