9.2.4 Safety Analysis

The assessment of safety will be based mainly on the frequency of adverse events. Other safety data (e.g., vital signs and special tests) will be summarized as appropriate.

Adverse events will be coded using a current MedDRA dictionary and summarized by presenting, for each treatment group, the number and percentage of subjects having any adverse event, having an adverse event in each body system (System Organ Class), and having each coded individual adverse event. Other adverse event information collected (e.g., severity/intensity or relationship to study medication) will be listed as appropriate.

Data from other tests will be listed, notable values will be flagged, and any other information collected will be listed as appropriate. No inferential statistical tests are planned for safety data but may be performed on an ad-hoc basis to highlight any comparisons that may warrant further consideration.

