Appendix D: Irritation Scoring

For the irritation assessment, the following scale will be utilized:

Numeric Grades:

- 0 = no evidence of irritation
- 1 = minimal erythema, barely perceptible
- 2 = definite erythema, readily visible; or minimal edema; or minimal papular response
- 3 = erythema and papules
- 4 = definite edema
- 5 = erythema, edema, and papules
- 6 = vesicular eruption
- 7 = strong reaction spreading beyond test site

All clinically significant skin responses observed with the test products or any score of 3 or higher will be reported as an adverse event.

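### A clinically significant laboratory change with no identified cause has no rule that puts it into the AE counts on which the safety assessment mainly rests

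*Combined protocol and SAP*

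**What the plan says.** Section 8.1 sets the recording rule for laboratory results: "Abnormal laboratory values or clinically significant changes in laboratory values are not adverse events, but the underlying reasons are". The exclusion covers clinically significant changes as well as trivial ones, and there is no fallback for a change whose reason is not established.

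Section 3.4 asks for a judgement on the same results: "Investigators will assess all out of range values as being clinically significant or not". No AE entry follows from a positive judgement.

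Section 9.2.4 sets the weight of the analysis: "The assessment of safety will be based mainly on the frequency of adverse events". AEs are tabulated by treatment group as subjects with any event, by system organ class and by coded term. For the rest it says "Other safety data (e.g., vital signs and special tests) will be summarized as appropriate" and "Data from other tests will be listed, notable values will be flagged, and any other information collected will be listed as appropriate". Laboratory results are not among the examples of data to be summarised, and no by-group count of clinically significant laboratory changes is specified.

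Section 8 requires AEs to be followed until they resolve or the condition is stable, and section 8.2 says the same for AEs and SAEs.

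**The concern.** The investigator is asked to pick out the laboratory results that matter, and the AE definition then excludes them unless a reason can be given. Counting the cause instead of the value is sensible when a cause is known, because it avoids recording one problem twice. It works badly when no cause is known. The finding then has neither a diagnosis nor an entry of its own.

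Two things are at stake. First, the main comparison of safety between groups would not contain such a case. Second, the duty to follow the finding to resolution or stability would not apply, because the protocol attaches that duty to AEs. Both matter more in a small dose-escalation study, where single subjects carry weight.

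**Working it through.** The documents state no figure on this point, so there is none to reproduce. The check is to follow one case through the sections.

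1. **The case.** A subject has normal chemistry at Baseline and an out-of-range value at Week 4, with no symptoms, no diagnosis and no change of medication.
2. **Section 3.4.** The investigator classes the value as clinically significant. The section stops there.
3. **Section 8.** Laboratory results do feed into AE detection: "information derived from change in concomitant medications, laboratory analyses, and clinical observations will be evaluated for possible indications for side effects". This is surveillance. It does not say what to record if the evaluation finds no cause.
4. **Section 8.1.** The change itself is excluded by name. Only its reason may be recorded, and here none is identified. Section 8.1 also counts the reason for a change of medication as an AE, but no medication has changed. No AE results.
5. **Section 9.2.4.** With no AE record, the subject adds nothing to the AE counts and percentages for this finding. The value appears in a listing, flagged if notable, and possibly in a summary.
6. **Sections 8 and 8.2.** Follow-up to resolution or stability applies to AEs, so it does not apply here. The next scheduled laboratory sample is at Week 26/End of Study (sections 3.4.3 and 3.4.4), that is 26 − 4 = 22 weeks later for a subject who stays in the study. Section 6.1.9 adds blood samples at early termination, and section 6.1.10 allows unscheduled ones.

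**Contrast within the protocol.** For skin reactions, Appendix D gives an explicit threshold: "any score of 3 or higher will be reported as an adverse event". For laboratory findings there is none, although the investigator has already made the judgement on which one could be built.

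**Scale of one case.** Section 3.2 plans 24 subjects in each of the vehicle, 690 U and 1,100 U groups. One subject is 1/24 = 0.042, or 4.2 percentage points of a group's AE frequency. This is the weight of one case. It says nothing about how often a case would occur.

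**A point for the fix.** Section 8.1.2 defines mild, moderate and severe by the symptoms the subject has. A symptom-free laboratory finding recorded as an AE would have no grade under those definitions.

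**The case against.** The strongest reply is that the gap is narrow and the information is not lost. Section 8.1 does not demand a confirmed diagnosis, so a suspected reason could be entered. Section 8 covers observed as well as volunteered problems and lets a sign be recorded. A result that leads to a change of medication enters through the reason for that change. Laboratory data are a named safety measure in section 3.4, and the values go to both investigator and sponsor. With 72 subjects a flagged listing can be read in full, and no inferential safety tests are planned, so no test result would change. Recording causes instead of values is also a recognisable and clearly stated convention.

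Most of this stands, and it limits the point to changes that are asymptomatic, unexplained and untreated. It does not close the gap, because none of these provisions turns such a case into an AE. A flagged line in a listing is not a by-group rate.

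A reader might infer three stronger things that the documents do not support.

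- *That the Week 4 review before escalation would miss laboratory toxicity.* Sections 3.1 and 7.3 call for a safety review and do not limit it to AE data, and the sponsor has the laboratory values. Nor is it shown that an asymptomatic laboratory change would meet a halting rule in 7.3 even if it were recorded as an AE.
- *That such a finding could never be rechecked.* The Week 26, early-termination and unscheduled samples allow it. What is missing is a requirement to follow it.
- *That a likely number of lost cases can be stated.* The documents give no incidence of unexplained clinically significant changes. Any probability would only restate an assumed rate.

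**Conclusion.** The point holds in a limited form. As section 8.1 is written, a laboratory change that the investigator judges clinically significant but that is asymptomatic, unexplained and untreated stays out of the by-group AE frequencies and outside the AE follow-up requirement. It remains in the laboratory data. This is the effect of a stated rule, not of missing detail.

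The effect on AE rates cannot be quantified from the documents. The conclusion assumes that 8.1 is followed literally and that the investigator enters no suspected reason or accompanying sign. It is a cheap improvement, not a flaw that undermines the safety assessment.

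**What to change.** Make three short changes.

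1. **Section 8.1:** state that a laboratory change judged clinically significant by the investigator and worsened from Baseline is recorded as an AE under its diagnosis or, if none is established, under the laboratory finding itself. Keep the exclusion for changes judged not clinically significant.
2. **Section 8.1.2:** add a line on how a symptom-free laboratory finding is graded for severity.
3. **Section 9.2.4, or the separate SAP that section 9.5 announces:** add a count and percentage, by treatment group, of subjects with a clinically significant laboratory change.

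The third change alone would make such cases visible by group, but it would leave them outside the AE follow-up. The changes use a judgement that is already collected and add no scheduled visit or sample. The downside is a few more reported AEs, which could fall in any arm.

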8.1.1 Relationship to Study Drug

The following definitions to assess the causal relationship between an adverse event and the study drug should be used:

Not Related: The event is clearly related to other factors such as a subject's clinical state, therapeutic interventions or concomitant medications.

Possibly Related: The event has a reasonable temporal relationship to study drug administration and follows a known response pattern to the study drug. However, a potential alternate etiology may be responsible for the event.

Related: The event follows a clear-cut temporal sequence from the time of drug administration and follows a known response pattern to the study drug and either occurs immediately following study drug administration, or improves on stopping the drug, or reappears on repeat exposure.

8.1.2 Adverse Event Severity

Mild: A mild adverse event is one that the symptoms are barely noticeable to a subject. It does not influence performance or prevent a subject from carrying on with normal life activities.

Moderate: A moderate adverse event is one that the symptoms make the subject uncomfortable and causes some impairment to normal life activities. Treatment for symptom(s) may be required.

Severe: A severe adverse event is one that the symptoms cause severe discomfort to the subject and severely limits the subject's normal daily activities. Treatment for symptom(s) is given.

Note that "serious" and "severe" are not synonymous. A serious adverse event must fulfill the requirements listed in the definition below, see section 8.1.3.

When intensity changes or occurs more frequently than once a day, the maximum intensity for the event will be listed. If the intensity category changes over a number of days, then these mini-events or changes will be recorded separately (i.e., having distinct onset days).

8.1.3 Serious Adverse Events

A serious adverse event is an event that is:

- fatal / results in death
- life-threatening
- results in persistent or significant disability/incapacity
- requires or prolongs subject hospitalization or
- is a congenital anomaly or birth defect

Life Threatening is defined as an event in which a subject is at risk of death at the time of the event. It does not refer to an event that hypothetically might have caused death if it was more severe.

Death: The death of an enrolled subject is not an event, but an outcome. It is the event that resulted in a fatal outcome that must be reported.

Disability is defined as a substantial disruption of a person's ability to conduct normal life functions.

ANY SERIOUS ADVERSE EVENT, INCLUDING DEATH DUE TO ANY CAUSE, WHICH OCCURS DURING THIS INVESTIGATION, WHETHER OR NOT RELATED TO THE STUDY MEDICATION, MUST BE REPORTED **IMMEDIATELY** (DURING NORMAL BUSINESS HOURS, 9 AM TO 5 PM, ET) TO THE SPONSOR/MEDICAL MONITOR.

Any serious adverse event should be reported to Eirion Therapeutics by telephone and e-mail within 24 hours of the event. The call should be followed-up with the completion of the written SAE report form within five days of receiving firsthand knowledge of the event. Full details of the event, any sequelae and an assessment of the relationship to the study drug must be provided in the report. Any serious adverse event must also be reported to the Institutional Review Board within 48 hours of receiving firsthand knowledge of the event and a copy of this SAE report must be sent to Eirion Therapeutics. The original SAE report form should be maintained in the Regulatory Binder. It is the Sponsor's responsibility to fulfill reporting obligations to the FDA.

Reports of serious adverse events should be made by telephone to:

Eirion Therapeutics Clinical Development Department: [contact]
or [contact]

Serious adverse events associated with the use of the study medication will be reported to appropriate regulatory agencies, investigators, and the IRB by the Sponsor.

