7.3 Stopping Rules

The study is designed as a sequential, overlapping cohort, dose-escalation trial. Enrollment will be halted after each cohort until a safety review has been completed.

- Enrollment will be halted in the event that one serious adverse event (SAE), considered to be probably or definitely related to the administration of study medication, is observed.
- Enrollment will be halted in the event that one AE is observed considered to be indicative of distant spread of study medication or unintended exposure to other beings.
- The Sponsor may stop the study in its entirety or discontinue individual study centers at its discretion for any reason or, e.g. if it is observed that the protocol or sound clinical practices are not being followed, or for any other reasons.

The study protocol calls for only one single application of study medication at Baseline (Week 0). Since there is no continuous treatment, no stopping rules for subjects are

applicable and subjects will be encouraged to participate in the study until the scheduled termination visit at Week 26.

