11 QUALITY CONTROL AND QUALITY ASSURANCE

The investigator will allow Eirion Therapeutics or their designated affiliates to periodically audit, at mutually convenient times during the study and after the study has been completed, all source documents and corresponding portions of office, hospital, and laboratory records of each subject. The monitoring visits will provide Eirion Therapeutics with the opportunity to confirm the rights and safety of the subjects, ensure the confidentiality of the data and subject's identification, evaluate the progress of the study, verify the accuracy and completeness of the eCRFs, assure compliance with protocol requirements, applicable FDA regulations, IRB and ICH-GCP Guidelines, confirm that investigator's obligations are being fulfilled, and resolve any inconsistencies in the study records. The sponsor may stop the study if it is observed that the protocol or sound clinical practices are not being followed.

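### The closed five-item definition of a serious adverse event has no criterion for an important medical event treated to prevent a listed outcome, so such an event carries no expedited report.

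*Combined protocol and SAP*

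**What the plan says.** Section 8.1.3 opens with "A serious adverse event is an event that is" and then gives five items: "fatal / results in death"; life-threatening; "results in persistent or significant disability/incapacity"; "requires or prolongs subject hospitalization or"; and congenital anomaly or birth defect. The lead-in does not present these as examples. Life-threatening is confined to risk of death at the time: "It does not refer to an event that hypothetically might have caused death if it was more severe". Section 8.1.2 makes the list binding: "A serious adverse event must fulfill the requirements listed in the definition below, see section 8.1.3". Section 8 has seriousness recorded in the eCRF by the same list.

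Several duties depend on that status. Under 8.1.3 the site tells the sponsor at once, and by telephone and e-mail within 24 hours, sends a written form within five days, and informs the IRB within 48 hours. Under Section 8 the sponsor reports serious events to the IRB and FDA within 10 working days. The first rule in Section 7.3 begins "Enrollment will be halted in the event that one serious adverse event (SAE") and goes on to require a judgement that the event is probably or definitely related to giving the study medication. The second rule in 7.3 stops enrolment for one adverse event of any seriousness, but only if it points to distant spread or to exposure of others.

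**The concern.** This is an out-patient trial of a changed needling device (Sections 2 and 3.1) used beside the eye. Section 4.1 allows that the device may raise bioavailability. Section 1 notes how close the site is to delicate organs, and Section 4.2 takes precautions against run-off. An eye, skin or allergic event that is treated effectively in the clinic is therefore foreseeable. If treatment works before the subject is at risk of death, significantly disabled or admitted, none of the five criteria is met, however important the event was.

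What is at stake is how quickly the sponsor and the IRB learn of it. The sponsor's freedom under 7.3 to stop the study at any time is useful only if someone is obliged to tell the sponsor in time.

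**Working it through.** No power or error-rate calculation applies. The check is a count of criteria, a trace of which rules depend on seriousness, and one piece of arithmetic on exposure.

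1. **Criteria.** Section 8.1.3 has five. The number that address an important medical event, or intervention to prevent a listed outcome, is zero. Sections 7.3, 8, 8.1, 8.1.2, 8.1.4 and 8.2.1 and Appendix D add none.

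2. **Neighbouring categories that might catch the event.**
   - Severity (8.1.2): a severe event is one with marked discomfort and limitation for which treatment is given. The same section says severe is not the same as serious.
   - Irritation (Appendix D): the top grade, 7, is a strong reaction extending past the test site. Any score of 3 or more is reported as an adverse event, with no clock attached.
   - Unanticipated problems (8 and 8.1.4): the parts dealing with adverse events also require the event to be serious, and no other meaning of the word is given. The remaining parts concern protocol changes, deviations and confidentiality.

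3. **Rules that depend on seriousness.**

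| Rule | Needs a serious event? |
|---|---|
| Immediate and 24-hour report to sponsor (8.1.3) | Yes |
| 48-hour report to IRB (8.1.3) | Yes |
| Unanticipated-problem report, adverse-event parts (8, 8.1.4) | Yes |
| First enrolment halt (7.3) | Yes, plus relatedness |
| Second enrolment halt (7.3) | No, but only distant spread or exposure of others |
| Safety review between cohorts (3.1, 7.3) | No |

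   Section 8 itself separates local from systemic spread, and Appendix B checks eye movement and lid droop. A local ocular effect can therefore lie outside the second halt rule. An event that does suggest distant spread stops enrolment, but it too has no reporting clock unless it meets one of the five criteria.

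4. **Exposure before the safety review.** From Section 3.2, each cohort has 12 vehicle + 24 active = 36 subjects, and two cohorts give 2 × 36 = 72. Section 3.1 places the review after the cohort is fully enrolled and has completed Week 4. If the event occurs in the first subject treated, up to 36 − 1 = 35 others can be dosed before that review. If it occurs late in enrolment, the number falls towards zero.

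5. **The halt rule.** Section 7.3 uses the grades probably and definitely related. Section 8.1.1 offers only Not Related, Possibly Related and Related. Its top grade also calls for a response pattern known for the drug, while 7.3 ties the halt to administration of the medication. An injury caused by the needling step alone might not satisfy either, even if it were classed as serious.

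**The case against.** The strongest reply is that these events are not lost. Section 8.1 has all adverse events recorded whatever their severity or relationship, 8.2 has them followed to resolution or a stable outcome, and the between-cohort review is not confined to serious events. The sponsor may stop at its discretion. The list, the eCRF and the triggers agree with one another, so on this definition the protocol does not contradict itself. All of this stands. It limits the point to timing within a cohort, but it supplies no timed duty to report.

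A reader might infer more than the text supports:

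- *That every important event managed without admission is outside the definition.* It is not. A reaction that puts the subject at risk of death is life-threatening even if treated in the clinic, and an eye injury that substantially disrupts normal functioning can meet the disability criterion.
- *That dose escalation can go ahead while the event lies unseen.* Cohort 2 waits for Cohort 1 to reach Week 4 and for a safety review.
- *That the serious-event report is the only prompt notice to the sponsor.* Section 8.2.1 also requires immediate notice of a pregnancy.
- *That the list breaches external rules.* Section 11 says that monitoring visits are to "assure compliance with protocol requirements, applicable FDA regulations, IRB and ICH-GCP Guidelines", and Section 8 refers generally to IRB and regulatory requirements. Those texts are not in the documents, so the comparison cannot be made here and is not relied on.
- *That a sixth criterion would by itself bring such events under the enrolment halt.* The relatedness condition in step 5 stands in the way.

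**Conclusion.** The gap is real and narrow. Followed as written, the protocol leaves an important medical event that is treated before it reaches a listed outcome without an expedited report to the sponsor or the IRB. The sponsor may therefore not hear of it promptly while the rest of a 36-subject cohort is dosed; 35 further subjects is the upper bound, and applies only if the first subject is affected. How often such events would occur cannot be computed from the documents, and no likelihood is claimed.

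The conclusion assumes that sites apply 8.1.3 as the closed list that 8.1.2 makes it, and that no site or sponsor procedure outside these documents imposes an earlier report. It does not depend on any outside definition. It is a cheap improvement to safety oversight that should be made; it is not a flaw that undermines the trial.

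**What to change.** Add a sixth criterion to 8.1.3 and to the SAE form: an important medical event that, in the judgement of the investigator or the sponsor, may jeopardize the subject or require intervention to prevent one of the other listed outcomes. The existing 24-hour and 48-hour timelines then apply to it, as does the seriousness condition in 8.1.4.

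Separately, reconcile the relatedness terms in 7.3 with the three-grade scale in 8.1.1 and with the amended 8.1.3. How the enrolment halt should apply to such events, including those caused by the needling step, is for the sponsor to state.

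The cost is one line in the definition, an edit to the form, and the wording needed for the reconciliation. The downside is somewhat more expedited reports and, because one related serious event halts enrolment, possibly more frequent pauses. Neither dosing nor the efficacy analysis is affected.
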